8.4.2 Secondary Endpoints/Other Endpoints

Frequency tables will be prepared for categorical variables, and continuous variables will be described by means of summary tables, which will include the median, mean, standard deviation, interquartile range, minimum, and maximum of each variable.

In addition to Bayesian methods, frequentist methods will be also calculated. Counts and percentages, with their corresponding exact confidence intervals, will be calculated for the binomial endpoints. Time-to-event variables and their set time estimates will be analysed according to the Kaplan-Meier method and Cox regressions.

Key secondary endpoint, time to confirmed negativisation in SARS-CoV-2 antigen test or RT-PCR Ct > 30, will be analysed according to the Kaplan-Meier method and Cox regressions following unstratified and stratified test as supportive analyses.

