EFFICACY EVALUATION CRITERIA	
Efficacy parameters include:
 
 • Mortality (all-cause and related to COVID-19); • COVID-19 signs and symptoms will be collected daily from Day 1 until the end of hospital care; thereafter at Days 4, 8 (±1), 15 (±1), 30 (±2), 45 (±2), and 60 (±3); • Clinical status is assessed using the WHO 11-point Clinical Progression Scale; • Lung function tests include fraction of inspired oxygen (FiO₂) (%), oxygen saturation (SpO₂), partial pressure of oxygen (PaO₂) (mmHg) [could be imputed from oxygen saturation (SpO₂)]. PaO₂/FiO₂ ratio will also be calculated (See Appendix 5 - Imputation of PaO₂/FiO₂ ratio); • SARS-CoV-2 quantitative real-time-reverse transcription polymerase chain reaction test (qRT-PCR) will be performed by central laboratory from oro-nasopharyngeal exudates on Day 1 before administration of the study drug and repeated at Days 4 (±1), 8 (±1), 15 (±1), 30 (±2), 45 (±2), and 60 (±3). Name of the variant will be collected if known; • SARS-CoV-2 Rapid Antigen test (RAT) will be performed every other day from Day 4 until discharge, and always at Days 1, 4 (±1), 8 (±1), 15 (±1), 30 (±2), 45 (±2), and 60 (±3); if RAT is positive at discharge, RAT should also be monitored on a weekly basis until negative. A

	
negative result should be confirmed with a second RAT within 48 h, by the investigator team;
 
 • Humoral response anti-SARS-CoV-2; • T-cell response against SARS-CoV-2; • Additional therapies for COVID-19; • Type and dates of oxygen support; • Radiological scores (chest X-ray, Brixia score; centrally assessed) (See Appendix 9 – Brixia Score); • Death date and reason; • Dates of discharge from ICU or hospital, and date of eventual re-admission; • Inflammatory and immunological biomarkers, including C-reactive protein (CRP), procalcitonin, lactate dehydrogenase (LDH), ferritin, neutrophil-to-lymphocyte ratio, ALC, D-Dimer, and multiplex cytokines assay; • Compliance with scheduled therapies for the underlying disease.
PHARMACOKINETIC (PK) EVALUATIONS	
PK analysis of plitidepsin concentration-time data will be performed in 30 patients using non-linear mixed-effects modelling. Individual PK parameters will be (See Section 7.6):
 
 • Plasma total area under the curve (AUC). • Plasma total clearance (CL).

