3.1 PRIMARY ENDPOINT

- *Efficacy primary endpoint*
 - 1-month[†] all-cause mortality rate. [†](Day 30 since randomisation).

3.2 KEY SECONDARY ENDPOINT.

- Time to confirmed negativisation in SARS-CoV-2 antigen test or RT-PCR Ct > 30.

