	ASSESSMENT/PROCEDURES	TIME
	for specific gravity, blood, pH, proteins, bilirubin, glucose, ketones, nitrites, and qualitative analysis of the sediment).	clinically indicated for AE evaluation. When applicable, these assessments should be performed before treatment administration.
Inflammatory and immunological biomarkers in blood (central laboratory)	Luminex® Multiplex cytokine assessment.	Days 1, 2, 4 (± 1).
Anti-SARS-CoV-2 (central laboratory)	IgG/M anti-protein S and N.	Day 1 previous to treatment administration.
	T-cell response (IFN- γ) to SARS-CoV-2 S-protein (Quantiferon®).	
Detection of SARS-CoV-2	qRT-PCR in oro/naso-pharyngeal exudates (central laboratory).	Day 1, 4 (± 1).
	Rapid Antigen Test (at site).	Day 1, 4 (± 1).
ECG**	Cardiac rhythm will be identified in ECG intervals of at least 30 seconds of duration, PR interval, QT interval (raw), heart rate and QRS complex, with specialist assessment/judgment of further evaluation if appropriate.	At screening or Day 1 (previous to treatment administration). Repeat on Day 4 (± 1), and whenever clinically indicated for AE evaluation.
Chest X-ray	Qualitative evaluation and Brixia score (See Appendix 9 – Brixia Score). (Submission to central review)	At screening or Day 1 (previous to treatment administration). Repeat whenever clinically indicated for AE evaluation.
ISARIC-4C deterioration score	Appendix 4	At screening or Day 1 (previous to treatment administration).
Pharmacokinetics (central laboratory)	(See details in Section 7.6).	Days 1, 3, 4 (see details in Section 7.6).
Antiviral Treatment administration	(See details in Section 6.1).	Days 1-3 in the experimental arm.⁹

	ASSESSMENT/PROCEDURES	TIME
		From Day 1 (date of randomisation) to the last dose of the antiviral therapy in the control arm. [¥]
Survival status		Throughout the treatment period.
Hospitalisation status		Throughout the treatment period.
Adverse events	As per NCI-CTCAE v.5***	Throughout the treatment period.

* Central laboratory for all the tests, except for screening.

** Triplicate.

*** The “AE form” will be used to report signs and symptoms and medical history in case of any significant change (improvement or worsening) during the study, as well as for events that occur after the first drug infusion or any event related to a study procedure within the study period (according to ICH guidelines).

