7. STUDY EVALUATIONS

7.1 EFFICACY

7.1.1 Test for COVID-19

A SARS-CoV-2 Rapid Antigen Test, provided by the Sponsor, will also be performed at the site by the research team on Day 4 until discharge, and always at Days 1, 4 (± 1 day), 8 (± 1 day), 15 (± 1 day), 30 (± 2 days), 45 (± 2 days), and 60 (± 3 days); if RAT is positive at discharge, RAT should also be monitored on a weekly basis until negative. A negative result should be confirmed with a second RAT within 48 h, by the investigator team.

Quantitative PCR to assess viral load on Day 1 before initiation of treatment and on Days 4 (± 1 day), 8 (± 1 day), 15 (± 1 day), 30 (± 2 days), 45 (± 2 days), and 60 (± 3 days) (see [Appendix 13 - Schedule of Assessments and Procedures](#)), will be performed by a central laboratory. Based on these assessments, changes in viral load respect to Day 1 will be calculated for each patient. The proportion of patients with either $> 2 \log 10$ reductions or undetectable SARS-CoV-2 on each time point will also be assessed.

Details regarding the collection, processing, storage, and shipment of oro-nasopharyngeal samples for qPCR testing will be provided to each investigational site before initiation of the study in the form of a laboratory manual. All oro-nasopharyngeal samples for qPCR must be

processed and shipped as specified in the laboratory manual to maintain sample integrity. Any deviations from the processing steps (e.g., sample collection and processing steps, interim storage, or shipping conditions), including any actions taken, must be documented and reported to the Sponsor. On a case-by-case basis, the Sponsor may make a determination as to whether sample integrity has been compromised. Any deviation from the specified sample handling procedure that results in compromised sample integrity will be considered a protocol deviation.

Samples will be analysed using validated analytical methods, as approved by the Sponsor.

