8.5 SUMMARY OF ESTIMANDS AND STATISTICAL TESTS

The primary estimand corresponding to the primary endpoint is defined as:

Treatment: Participants will be randomised to receive plitidepsin versus control in each group.

Population: Participants as defined through the inclusion and exclusion criteria, who have been randomised to the trial and who have taken at least 1 dose of study treatment (plitidepsin or control).

Variable:

–1-month all-cause mortality rate (Day 30 since randomisation).

Intercurrent events:

–The participant's data are collected and included in the analysis without regard for treatment discontinuation (treatment-policy strategy).

–In the event of the participant initiating another non-protocol therapy, 1-month all-cause mortality rate will be evaluated regardless of initiation of new non-protocol therapy (treatment-policy strategy).

Population level summary: the posterior probability associated for the odds ratio of 1-month all-cause mortality rate from a Bayesian logistic regression for each group comparison.

Below a summary table where main/supportive analyses are described. P values except for the primary analysis have to be considered as exploratory and nominal values will be shown.

Endpoints	Analyses
Efficacy primary endpoint	
1-month all-cause mortality rate.	
 -Bayesian odds ratio (primary analysis by CHBM) -Bayesian odds ratio (Berry's Method) - Unstratified odds ratio (Univariate Logistic regression) - Stratified odds ratio (Multivariate Logistic regression)
Key secondary endpoint	
Time to confirmed negativisation in SARS-CoV-2 antigen test or RT-PCR Ct > 30.	
 -Kaplan-Meier (unstratified and stratified) -Cox regression (unstratified and stratified)
Efficacy secondary endpoints	
Time to sustained end of COVID-related hospital care from the time of randomisation. Sustained discharge is defined as no subsequent admission within 30 days of initial end of hospital care [up to day 60 (± 3)], related to either COVID-19 or COVID-19 therapy	
 -Kaplan-Meier (unstratified) -Cox regression (unstratified)
Time to sustained improvement (defined in Section 7.1.3) and resolution of selected COVID signs/symptoms (See Appendix 10 - COVID-19 signs/symptoms checklist).	
 -Kaplan-Meier (unstratified) -Cox regression (unstratified)

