11.6.2 Key Secondary Estimand

The key secondary estimand corresponding to the key secondary endpoint is defined as:

Treatment: Participants will be randomised to receive plitidepsin versus control in each group.

Population: Participants as defined through the inclusion and exclusion criteria, who have been randomised to the trial and who have taken at least 1 dose of study treatment (plitidepsin or control).

Variable:

–Time to confirmed negativisation in SARS-CoV-2 antigen test or RT-PCR Ct > 30 calculated as date/time of survival event – first dose date/time of Investigational Product administration.

Intercurrent events:

- The participant's data are collected and included in the analysis without regard for treatment discontinuation (treatment-policy strategy).
- In the event of the participant initiating another non-protocol therapy, time to confirmed negativisation will be evaluated regardless of initiation of new non-protocol therapy (treatment-policy strategy).

Population level summary: the hazard ratio from a Cox regression for each group comparison including point estimate and confidence interval will be shown.

<NOTE: Due to the premature study closure no complex specific outputs will be generated and descriptive data will be shown>.

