11.8 Summary of Statistical Tests

All the main characteristics for estimands to fulfill study objectives will be defined as footnotes in each table following a similar structure than primary estimand definition. Below it can be found the endpoints to measure the variable definition and the analysis method to be used. Treatment attribute is maintained as 'participants will be randomised to receive plitidepsin versus control in each group' whereas applicable and sensitivity analyses according populations defined in 8.5 will be calculated. For intercurrent events, while applicable, a treatment-policy strategy as defined for the primary estimand will be followed.

Table 3 Summary of statistical tests

Endpoints	Analyses	Population
Efficacy primary endpoint		
1-month all-cause mortality rate.	-Frequencies	-FAS population
Key secondary endpoint		
Time to confirmed negativisation in SARS-CoV-2 antigen test or RT-PCR Ct > 30.	-Kaplan-Meier (unstratified)	-FAS population

Endpoints	Analyses	Population
Efficacy secondary endpoints		
Time to sustained end of COVID-related hospital care from the time of randomisation. Sustained discharge is defined as no subsequent admission within 30 days of initial end of hospital care [up to day 60 (± 3)], related to either COVID-19 or COVID-19 therapy	-Kaplan-Meier (unstratified)	-FAS population
Time to sustained improvement (defined in Protocol Section 7.1.3) and resolution of selected COVID signs/symptoms (See Protocol Appendix 10 - COVID-19 signs/symptoms checklist).	-Kaplan-Meier (unstratified)	-FAS population
Distribution of patients according to their clinical status by the 11-category WHO Clinical Progression Scale, at Days 4 (± 1), 8 (± 1), 15 (± 1), 30 (± 2), and 60 (± 3) (See Protocol Appendix 1 – 11-Point World Health Organization (WHO) Clinical Progression Scale).	-Frequencies	-FAS population
Percentage of patients requiring oxygen therapy on Days 4 (± 1), 8 (± 1), 15 (± 1), 30 (± 2), and 60 (± 3).	-Frequencies	-FAS population
Time to sustained discontinuation (i.e., at least 7 days) of oxygen supplementation.	-Kaplan-Meier (unstratified)	-FAS population
Safety secondary endpoints		
Treatment-emergent adverse events (TEAEs).	-Frequencies (severity grade by NCI-CTCAE v5)	-As treated population
TEAEs \geq grade 3 according to the National Cancer Institute	-Frequencies	-As treated population

Endpoints	Analyses	Population
[NCI]-Common Terminology Criteria for AEs (CTCAE v.5.0).		

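### Day 1 central viral load is collected but is not a covariate in the planned Cox model for time to viral clearance; adding it would be a nearly free improvement

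*Protocol*

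**What the plan says.** **Endpoint.** Protocol 3.2 defines the key secondary endpoint as "Time to confirmed negativisation in SARS-CoV-2 antigen test or RT-PCR Ct > 30". The objective (Protocol 2.2) is a comparison within each group.

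**Model.** Protocol 8.4.2 states that this endpoint "will be analysed according to the Kaplan-Meier method and Cox regressions following unstratified and stratified test as supportive analyses". The table in Protocol 8.5 lists the same two forms of Kaplan-Meier and Cox analysis and names no covariate. Protocol 5.6 gives the stratification factors: ISARIC-4C mortality score below 9 or at least 9 in every randomised group, plus graft type (Group 1) or underlying disease (Groups 2 and 3).

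**Baseline virology.** Protocol 7.1.1 schedules "Quantitative PCR to assess viral load on Day 1 before initiation of treatment". The synopsis says the assay "will be performed by central laboratory from oro-nasopharyngeal exudates on Day 1 before administration of the study drug". In the planned analyses, Day 1 load serves as the reference value for other endpoints in Protocol 3.3.3: change in viral load, and time to undetectable load or a fall of more than 2 logs.

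**SAP v3.0, written after early closure.** The key secondary estimand (SAP 11.6.2) still says that "the hazard ratio from a Cox regression for each group comparison including point estimate and confidence interval will be shown", but a note below it restricts output to descriptive data. SAP 6.0 rules out formal tests while saying that the tables permit a numerical comparison of the arms. SAP 11.6 and Table 3 in 11.8 leave only an unstratified Kaplan-Meier analysis.

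**The concern.** The event occurs when virus falls below a detection threshold, so the starting distance from that threshold is an obvious candidate predictor. Inclusion criterion 3 accepts either Ct up to 30 or a positive antigen test, taken up to 3 days before randomisation. Patients may therefore start far from the threshold, close to it or, if they entered on antigen alone, already past it on Ct. The stratification factors capture general severity and underlying disease. Neither measures viral load.

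Two things are at stake. First, a Cox model that omits a strong predictor estimates a treatment hazard ratio closer to 1 and has less power than one that includes it. Second, with 20 patients per arm, a sizeable chance difference in Day 1 load is not rare. An unadjusted curve cannot separate an antiviral effect from a head start.

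**Working it through.** **1. No figure to reproduce.** The plan states no effect size, event count or power for this endpoint. Protocol 8.1 bases the group size on feasibility, and 8.5 treats p values outside the primary analysis as exploratory.

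**2. Inputs.**
- From the documents: 20 v 20 per group (Protocol 8.1) and follow-up to Day 60 (Protocol 3).
- Borrowed only to set the time scale: a control median of 17 days. This comes from the compassionate-use series (Protocol 1.2.1.3.3), where clearance meant Ct above 36, not 30.
- Assumed: exponential times, a treatment hazard ratio (HR) for clearance of 2.0 or 2.5, standardised Day 1 load with HR per SD from 1.0 (not prognostic) to 0.5, and a two-sided 5% Wald test.

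**3. What one group can support.** Schoenfeld power is Φ(√(d/4) × ln HR − 1.96). With d = 36 events, √9 = 3:
- HR 2.0: 3 × 0.693 − 1.96 = 0.12, power 55%.
- HR 2.5: 3 × 0.916 − 1.96 = 0.79, power 79%.

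For 80% power at HR 2.0, the events needed are 4 × (1.96 + 0.842)² / 0.693² = 66, more than a group of 40 can supply. Precision is therefore scarce.

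**4. Chance imbalance.** The difference in arm means of a standardised baseline has SD √(2/20) = 0.316.
- P(difference beyond 0.3 SD) = 2 × (1 − Φ(0.3/0.316)) = 34%.
- P(difference beyond 0.5 SD) = 2 × (1 − Φ(0.5/0.316)) = 11%.

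**5. Power without and with the covariate** (20 v 20, 4,000 simulated trials per row, about 36 to 38 events):

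| HR per SD of load | HR 2.0: unadjusted → adjusted | HR 2.5: unadjusted → adjusted |
|---|---|---|
| 1.0 | 54% → 53% | 77% → 77% |
| 0.8 | 51% → 54% | 74% → 76% |
| 0.65 | 45% → 53% | 66% → 75% |
| 0.5 | 35% → 51% | 54% → 73% |

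**6. The same on a correlation scale.** With exponential times, log time has residual variance π²/6 = 1.645, so correlation = |slope| / √(slope² + 1.645).
- Log-hazard slope −0.75 per SD: 0.75/1.486 = 0.50. Repeated runs at HR 2.5 give 51-55% unadjusted and 74% adjusted.
- Slope −0.4: 0.4/1.344 = 0.30. At HR 2.5, about 70% unadjusted and 77% adjusted.
- Pooled over 120 patients at HR 1.7 with slope −0.4: about 70% to 78%.

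At correlation 0.5, a true conditional HR of 2.5 is estimated at about 2.0 unadjusted and 2.6 adjusted.

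**7. Type I error.** With no treatment effect, rejection over all randomisations is 5.0-6.0% unadjusted and 5.3-6.1% adjusted. Among trials with a Day 1 difference beyond 0.5 SD (about 450 to 470 per scenario, so roughly ±1 to 2 points of simulation error), the unadjusted rate rises to 11% (HR per SD 0.65) or 15% (0.5). The adjusted rate stays at about 5-6%.

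**The case against.** **The analysis will not be run.** SAP v3.0 withdraws the Cox output and all tests for this endpoint. A reader might infer that the reported trial loses power through this omission. The documents do not support that: power has no meaning where no test is made, and 20 v 20 was a target that low recruitment in cohorts 1 and 3 (SAP 11.6) kept out of reach. This stands. The power argument concerns the protocol's plan only.

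**Unadjusted does not mean biased.** A reader might also infer that the planned hazard ratio is invalid. It is not. The test keeps its size over randomisations, and the unadjusted and adjusted hazard ratios are different quantities (marginal and conditional). The false-positive excess in step 7 is conditional on an observed imbalance. This stands too.

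**SAP v3.0 already reports virology.** SAP 11.2 lists the SARS-CoV-2 test among baseline items, 11.0 plans listings and viral-load figures over time, and Table 3 keeps change from Day 1. It would be wrong to say that baseline virology is ignored. But nothing commits to Day 1 quantitative load by arm next to the clearance curves, or says that those curves are unadjusted.

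**Load may predict less than expected.** The endpoint can be met on antigen alone. That test is repeated every other day during admission, while PCR is done only on scheduled days. On-site antigen results may drive many events. This is a fair reason to keep the no-gain end of the range in view.

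**An adjusted hazard ratio may be unstable** in the poorly recruited cohorts. Accepted; the fix allows for it.

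**Conclusion.** The point holds as a nearly free improvement to the protocol's plan, not as an error that invalidates it. A pre-treatment, centrally measured candidate predictor is scheduled in the protocol, and neither form of the key secondary Cox model uses it.

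The size is conditional. Per group of 40, the gain is about 0 to 20 power points, depending on a prognostic strength and a treatment effect that the documents do not give. If load is not prognostic, the loss is at most about one point. At 20 v 20, about one randomisation in nine (11%) would leave the arms more than 0.5 SD apart on Day 1 load.

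Under SAP v3.0 what remains is a matter of presentation. SAP 6.0 invites a numerical comparison of arms through unadjusted curves in small groups, where chance imbalance is likelier than at 20 v 20.

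**What to change.** **Protocol 8.4.2 and 8.5, and the estimand in SAP 11.6.2.** Pre-specify Day 1 central viral load (log10, one continuous term) as a covariate in the main Cox model for the key secondary endpoint, and keep the unadjusted hazard ratio as supportive. State in advance how a missing or unquantifiable Day 1 value is handled. A screening Ct is not a clean substitute: it may be up to 3 days old, may come from a different assay, and may not exist for patients who entered on antigen alone.

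**SAP v3.0.** Tabulate Day 1 viral load by arm and group beside the Kaplan-Meier output for this endpoint, and label the curves unadjusted. Where numbers allow, give the adjusted hazard ratio with its interval as a descriptive figure, without a test. Omit it in cohorts too small for a stable estimate.

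**Cost.** A few lines of wording, one degree of freedom, and one variable already scheduled for collection. No new visits, samples or patients are needed.

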8.4.3 Safety Analysis

Safety analyses will be based on the As Treated Population. All safety parameters will be summarised and also listed by patient.

Treatment-emergent Adverse Events: The verbatim terms used in the eCRF by investigators to identify TEAEs will be coded using the Medical Dictionary for Regulatory Activities (MedDRA) and will be graded according to NCI CTCAE version 5.0. Treatment-emergent AEs will be summarised by MedDRA system organ class and preferred term. For each TEAE, the percentage of subjects who experience at least 1 occurrence of the TEAE will be summarised overall and by treatment group. The SAEs, AEs of special interest, and deaths will be listed. All TEAEs resulting in discontinuation of study treatment will be listed and summarised by system organ class/preferred term.

AEs, SAEs, deaths, laboratory evaluations, and study drug discontinuations due to AEs will be tabulated in a descriptive way. Counts and percentages will be used for categorical variables, and summary tables will be used for continuous variables.

Any treatment-related adverse events, treatment-emergent adverse events of special interest, and SAEs that will be measured daily until resolution or stabilisation to at least Grade 1, or to an acceptable level according to the investigator and the sponsor of his/her designated representative.

Clinical Laboratory Tests: Laboratory data will be summarised by type of laboratory test. The worst toxicity grade will be tabulated. Parameters with predefined NCI CTCAE version 5.0 toxicity grades will be summarised. Change from baseline to the worst TEAE grade experienced by the subject during the study will be provided as shift tables.

